Because some subjects will receive LMTM for the first time in this study, the initial safety assessments will be made after 2 weeks. Thereafter, safety assessments will be made approximately every 3 months. Investigators are encouraged to continue with their routine clinical assessment of subjects consistent with good clinical practice to evaluate continued benefit from study participation.

Safety assessments are guided by the accruing safety information in the ongoing double-blind studies. The majority of the safety evaluations made in the double-blind studies will continue; specifically, intervening medical history, adverse events, and concomitant medication use will be assessed and recorded; seated blood pressure and pulse as well as body weight will be measured; clinical laboratory testing will be performed, including serum pregnancy testing in women of childbearing potential; 12-lead electrocardiograms (ECGs) will be monitored; and targeted physical and neurological examinations will be performed. The rationale for not mandating routine pulse co-oximetry measurement,

assessment of the potential for suicide or self-harm, and magnetic resonance imaging (MRI) for amyloid related imaging abnormalities (ARIA) is given below:

- Routine pulse co-oximetry has been included in all studies performed to date. As of 17 August 2015, 6 subjects (< 1%) in the ongoing Phase 3 trials have had a methemoglobin value >3.5% (the pre-specified threshold for possible clinical significance); all were isolated values, the highest of which was 8%. Relevant laboratory-related adverse events of special interest (AESIs) have been reported in only 5 subjects (< 1%): positive Heinz bodies (without other evidence of hemolytic anemia, considered a false positive due to a prolonged delay in preparing the slides for testing); hemolytic anemia (Heinz body negative, recovered with treatment interruption); and 3 reports of isolated increased methemoglobin. Pulse co-oximeters will not be routinely provided to sites and no specific monitoring is mandated in this open-label extension study protocol.

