The first on-treatment visit will occur approximately 2 weeks after Visit 1 (designated Visit 2) for the initial post-treatment safety assessment. Thereafter, subjects will be seen in the clinic at approximately every 13 weeks (relative to Baseline). Required assessments will be performed at all visits as described in the Schedule of Assessments in Section 4.4 and, for further detail, in Section 7; additional optional safety assessments are also described. Caregivers will be contacted by telephone at the mid-point between Visits 2 and 3; they will also be asked to contact the investigator in response to any safety concern. An unscheduled visit will be arranged to assess the subject as needed.

Resource utilization and quality of life will be evaluated as described in Section 8.

Continued participation will be re-evaluated approximately every 12 months on the basis of safety, tolerability, and continued benefit as judged by the investigator. Subjects deemed eligible for continued treatment (and/or their caregivers) must provide informed consent for re-enrollment. Subjects for whom consent is not provided consistent with national requirements and IRB/EC approval will be discontinued.

For subjects who cease to take LMTM, a post-treatment follow-up visit 4 weeks after the last dose of study drug is to be scheduled, regardless of the reason for discontinuation. Subjects who fail to complete the initial 12-month extension period will not be eligible to continue to receive treatment during any subsequent extension period.

A schematic representation of the first 12 months of the study is provided in Figure 4-1.

Figure 4-1 Schematic Representation of Study (First 12 Months)

	← Open-Label Treatment → LMTM 200 mg/day initial dose and flexible dosing thereafter (to max. 300 mg/day and min. 100 mg/day ^a) (52 weeks)							← Follow up → (4 weeks after last dose)	
	First dose of open-label treatment ↓					Last dose ^b ↓		Follow up Visit ^c ↓	
Visit	↑ 1	↑ 2 ^a	(T) ^d	↑ 3 ^a	↑ 4	↑ 5	↑ 6	↑ --	
Week	0	2	6	13	26	39	52	56	
Day (± days)	1	15 (3)	43 (14)	92 (14)	183 (14)	274 (14)	365 (14)	393 (14)	

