The majority of the safety assessments (described further in Section 7) will be repeated at each visit, *i.e.*, approximately 2 weeks post-Baseline and at visits occurring approximately every 3 months (13 weeks) relative to Baseline. These assessments include adverse event and concomitant medication recording, seated blood pressure and pulse, body weight, clinical laboratory testing (*e.g.*, hematology and serum chemistry panels), serum pregnancy testing in women of childbearing potential, and targeted physical and neurological examinations. The 12-lead ECGs will be obtained approximately every 6 months (26 weeks) relative to Baseline. Throughout the assessments for safety, the investigator is to be cognizant of the potential for serotonin toxicity, taking the MMSE into consideration as well.

The EQ-5D-5L, applied to the subject and to the caregiver on behalf of the subject, will be evaluated at Baseline (as it is not used in the Phase 3 studies of prior participation). The RUD-Lite will be also be evaluated at Baseline if not available from within the prior 42 days. These evaluations will be repeated approximately every 6 months (26 weeks) relative to Baseline.

The same aforementioned 13-week and 26-week schedules of in-clinic assessments will be maintained for continued treatment beyond the first 12 months (if there is re-consent at Visit 6), with no requirement for the Week 2 visit or Week 6 telephone contact in the second or any subsequent year of participation. Continued treatment will be restricted to those subjects for whom continued benefit is expected by the investigator to outweigh risk and informed consent is provided.

For subjects who do not re-enroll for a subsequent extension of treatment, identified end of treatment evaluations will be performed at the final on-treatment visit (*e.g.*, Visit 6). If a subject discontinues prematurely, an early termination visit should be conducted at which time all assessments identified for Visit 6 should be performed.

Post-treatment safety assessments will be conducted at a follow-up visit, to be scheduled to occur approximately 4 weeks after the last dose of study drug for all subjects who cease to take LMTM (regardless of the reason for discontinuation).

A schedule of assessments is shown in Table 4-1. Assessments are listed by visit in Appendix A: Assessments by Visit.

Table 4-1 Schedule of Assessments

Visit Name	Baseline ^a						First 12 Month Open-Label Extension ^b						Follow-up ^c

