4.7 Concomitant Medication

Current medications (and medications used since the last double-blind visit in the prior study of participation) will be recorded using the eCRF mapped from the originating double-blind study of prior participation. "Medication" is used to encompass prescription and over-the-counter drugs or biologics, vitamins used in supra-pharmacologic doses, alternative pharmacotherapies for dementia, medical foods, and for women, forms of contraception. At each scheduled or unscheduled visit, and at each telephone contact, any changes to existing concomitant medications and any new concomitant medications will be reviewed and recorded.

It is desirable, but not mandatory, that concomitant medications identified at Baseline be maintained at a constant dose for the duration of the study if clinically indicated. The investigator should evaluate any changes in the dose of existing concomitant medications and/or initiation of new concomitant medications, and the medical monitor should be contacted to discuss any concerns as needed. The date of commencement, dose, and date of any change of dose of concomitant medications are to be recorded in the eCRF.

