4.7.1 Dementia Medication

Subjects are allowed to take an AChEI and/or memantine, a medical food (*e.g.*, Axona, Souvenaid) or a stable dose of alternative pharmacotherapy for dementia (*e.g.*, Vitamin E, folate [in doses up to 5 mg/day; doses of approximately 1 mg/day in the management of

folate deficiency are acceptable], a specific neurocognitive vitamin formulation [such as NeuroVits comprising 20 mg Vitamin B₆, 1 mg Vitamin B₁₂, 0.8 mg folate], ginkgo biloba, hormone replacement therapy, treatments related to coconut oil, or circumin). Ideally, the dosage and time of dosing should remain unchanged during participation in the study. There are no restrictions for other non-pharmacological treatments during the treatment period.

Results suggest that MT may inhibit cytochrome P450 3A4 (CYP3A4), an enzyme system that is involved in the metabolism of two of the AChEIs allowed in the study, donepezil and galantamine. Because drug-drug interaction studies have not been performed with these drugs, it is not known whether systemic exposure to either of these drugs will increase or by how much. Therefore, subjects receiving these drugs should be monitored and if adverse events suggest an increase in systemic exposure, dose adjustment of donepezil or galantamine may be considered. If any change in dose occurs for whatever reason, the subject may continue on study drug unless it is judged to pose a risk to the subject.

4.7.2 *Drugs with Serotonergic Potential*

The oxidized form of MT (MT⁺) is an inhibitor of MAO A and B *in vitro*, and the investigator should be aware of the potential for drug interaction resulting in serotonin syndrome (toxicity). Recent (within five to seven plasma half-lives) or current treatment with medications identified by FDA in an October 2011 Safety Alert (augmented to include drugs not approved in the United States) should be undertaken only if the potential benefit is judged to outweigh the risk. Refer to the Investigator's Brochure for a list (not exhaustive) of such medications and their plasma half-lives (majority taken from U.S. approved product labeling). It should be noted that some of these are available without prescription and their use should also be recorded in the eCRF.

Drugs with serotonergic potential may be initiated after Visit 3 (Week 13) provided potential benefit is judged by the investigator to outweigh risk. The subject's general practitioner will be informed of the potential risk.

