6.2.3.1 Hemolytic Anemia

When there are clinical symptoms and/or laboratory signs of hemolytic anemia, dosing should be discontinued. Clinical symptoms are described in Section 7.1.3.1 and laboratory signs are described in Section 7.3.2. Follow-up laboratory monitoring is also

⁵ Administrative reasons (or other reasons not related to safety) are not to be considered safety reasons warranting treatment discontinuation.

described in Section 7.3.2. The medical monitor should be contacted to discuss whether or not resumption of dosing is indicated or for any other questions.

6.2.3.2 *Serotonin Syndrome*

Subjects are to be monitored at each visit by a medically qualified person for signs and symptoms indicative of potential serotonin toxicity, especially when initiating LMTM in this study or any medication with serotonergic potential. At each post-Baseline visit, subjects are to be evaluated by targeted physical and neurological examination and measurement of temperature, respiratory rate, blood pressure, and pulse (see Section 7.1.3.2 for guidance on assessment). Should serotonin syndrome (toxicity) be suspected clinically, treatment should be immediately discontinued. The event should be reported as an AESI and the medical monitor should be contacted for further guidance on subject management.

6.2.3.3 *Other Safety Reasons Requiring Dose Adjustment*

Treatment should be discontinued if the following treatment-emergent change occurs on ECG (based on the means of the three recordings) without other explanatory cause:

- QTcF interval > 500 msec: repeat ECGs should be obtained, in triplicate, within 2 weeks; if confirmed by the mean of the repeat ECGs, study drug should be discontinued pending further evaluation.

Other clinically significant changes in the ECG should be discussed with the medical monitor.

If renal concerns arise and the calculated creatinine clearance is < 30 mL/min, study drug should be discontinued.

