7 ASSESSMENT OF SAFETY

Safety will be assessed over time by means of adverse events (AEs) and concomitant medication recording; clinical laboratory tests of blood (*e.g.*, hematology and chemistry panels); vital sign measurements; 12-lead ECGs; and targeted physical and neurological examinations.

Assessments to be performed in the clinic are described in the subsections that follow. At an intervening time between Visit 2 and Visit 3 (approximately 6 weeks after Baseline), caregivers of subjects are to be contacted by telephone. An unscheduled visit is to take place if needed in response to a safety concern.

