7.1.3.2 Serotonin Syndrome (Toxicity)

Subjects are to be monitored for signs and symptoms indicative of potential serotonin toxicity, especially when initiating LMTM in this study or any medication with serotonergic potential. At each post-Baseline visit, subjects are to be evaluated by a medically qualified person by targeted physical and neurological examination and measurement of temperature, respiratory rate, blood pressure, and pulse. Results of the MMSE should also be taken into consideration. The evaluation should focus on detecting

signs and symptoms of serotonin syndrome (or serotonin toxicity) that include mental changes (confusion, hyperactivity, memory problems not attributed to underlying condition), muscle twitching, excessive sweating, shivering or shaking, diarrhea, trouble with coordination, and/or fever. A further guide is provided below.

Table 7-1 Overview of Monitoring and Management of Serotonin Syndrome (Toxicity)

Signs and Symptoms of Serotonin Toxicity	Monitoring at Each Clinic Visit	Action

Any one of the following:
 
Autonomic findings (temperature ≥ 38 °C, diaphoresis, shivering, tachypnea/dyspnea, diarrhea, hypertension or hypotension)
 
Neuromuscular changes (tremor; hyperreflexia; spontaneous, inducible, or ocular clonus; muscle rigidity¹; hypertonia; dizziness; incoordination; or mydriasis)
 
Other central nervous system changes (agitation/akathisia, elevated mood, insomnia)
	Oral (sublingual) temperature ²	
Discontinue study drug
 
Appropriate medical management to be undertaken
 
Report to Medical Monitor as AESI

	Seated blood pressure and pulse	
	Targeted PE and neurological examination, focused on the following: deep-tendon reflexes, clonus, and muscle rigidity; size and reactivity of pupils; dryness of oral mucosa; intensity of bowel sounds; skin color; and presence or absence of diaphoresis	
	MMSE (Baseline ³ , Weeks 26, 52, at the 4-week follow-up visit, and as needed to respond to changes)	

¹ Muscle rigidity can overwhelm other neuromuscular findings and mask the diagnosis

² Oral (sublingual) temperature measurements are preferable; aural temperature is an acceptable alternative (use of alternate measurement is to be noted in the eCRF)

³ MMSE to be rated at Baseline if not available from within the prior 42 days in the previous study of participation

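### A serotonergic drug may be started only after Visit 3, when scheduled examinations are 91 days apart and no call remains, although the protocol stresses serotonin-toxicity monitoring at such starts

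*Protocol*

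**What the plan says.** **When a start is allowed.** Protocol Section 4.7.2: "Drugs with serotonergic potential may be initiated after Visit 3 (Week 13) provided potential benefit is judged by the investigator to outweigh risk". The one further action it attaches to this is that the general practitioner is told of the risk. For monitoring it refers to Section 7.1.3.2, which applies whether or not the subject takes such a drug.

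**What monitoring is asked for.** Section 6.2.3.2: "Subjects are to be monitored at each visit by a medically qualified person for signs and symptoms indicative of potential serotonin toxicity". Section 7.1.3.2 adds the emphasis, "especially when initiating LMTM in this study or any medication with serotonergic potential", and Section 6.2.3.2 repeats it. Both sections then describe an examination and vital signs at each post-Baseline visit.

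**What the schedule provides.** Section 2 gives the reason for the Week 2 visit: "Because some subjects will receive LMTM for the first time in this study, the initial safety assessments will be made after 2 weeks". Section 4.1 adds the only scheduled call: "Caregivers will be contacted by telephone at the mid-point between Visits 2 and 3". After that, clinic visits are about 13 weeks apart. Section 4.4 continues this pattern into later years, "with no requirement for the Week 2 visit or Week 6 telephone contact in the second or any subsequent year of participation".

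**What happens between visits.** Section 7: "An unscheduled visit is to take place if needed in response to a safety concern". Section 4.1 asks caregivers to contact the investigator about safety concerns. Under Section 4.7, at each visit and call, "any changes to existing concomitant medications and any new concomitant medications will be reviewed and recorded".

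**Trazodone.** Footnote 3 to Section 4.7.5 requires monitoring steps when low-dose trazodone is used at bedtime. It gives neither their content nor their timing.

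**The concern.** The protocol names two occasions that call for particular vigilance: starting LMTM and starting a serotonergic drug. The first has dated contacts, an examination at Week 2 and a call at about Week 6. The second has none, and Section 4.7.2 places it in the part of the schedule where visits are furthest apart.

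Serotonin syndrome is one of the two adverse events of special interest, and Section 6.2.3.2 requires treatment to stop at once if it is suspected. Between visits, someone must first notice a sign. Several of the signs in Section 7.1.3.2, such as confusion, memory problems and agitation, are easily taken for the dementia itself, and that section asks for memory problems due to the underlying condition to be set aside. If nobody makes contact, the event reaches the site by recall, because Section 7.1 has adverse events elicited by asking how the subject has been since the previous visit. A sign that appears and resolves in the interval, and that nobody reports, would also be missing from the serotonin ratings.

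**Working it through.** The protocol gives no figure for this interval, so there is none to reproduce. The inputs are the scheduled study days in Protocol Figure 4-1: Day 1; Day 15 (±3); Day 43 (call, ±14); Days 92, 183, 274 and 365 (each ±14).

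**1. Nominal gaps between scheduled contacts**

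| From | To | Days |
|---|---|---|
| Visit 1 | Visit 2 | 15 − 1 = 14 |
| Visit 2 | call | 43 − 15 = 28 |
| call | Visit 3 | 92 − 43 = 49 |
| Visit 3 | Visit 4 | 183 − 92 = 91 |
| Visit 4 | Visit 5 | 274 − 183 = 91 |
| Visit 5 | Visit 6 | 365 − 274 = 91 |

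**2. Range for Visit 3 to Visit 4 within the windows**

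- Shortest: (183 − 14) − (92 + 14) = 169 − 106 = 63 days (9 weeks).
- Longest: (183 + 14) − (92 − 14) = 197 − 78 = 119 days (17 weeks).

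**3. Can the call fall after a permitted start?** The latest call is Day 43 + 14 = 57. The earliest Visit 3 is Day 92 − 14 = 78. Within the windows the call always comes before Visit 3, so it never covers a start allowed by Section 4.7.2.

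**4. Comparison with an LMTM start.** The first examination is 14 days after Visit 1, or 11 to 17 days with the ±3-day window.

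**5. Illustration for starts at other times.** Assume that starts are spread evenly between two visits 91 days apart. The mean wait for the next examination is 91/2 = 45.5 days, and 14/91 = 15.4% of subjects are examined within 14 days. The even spread is an assumption; the documents say nothing about when starts occur.

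**6. Is there another timed contact?** Section 4.7.2 ties neither a visit nor a call to the start. Appendix A includes a serotonin assessment at unscheduled visits, but these are held in response to a safety concern. Section 4.7 asks the investigator to evaluate new medications and to contact the medical monitor about concerns as needed. None of these sets a date.

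**The case against.** **Safeguards exist, and a reader might infer otherwise.** It would be wrong to conclude that subjects are unmonitored after a serotonergic start. Caregivers are asked to report concerns, are selected under Section 5.1 for enough contact to do so, and can prompt an unscheduled visit; the medical monitor is available. It would also be wrong to conclude that serotonin ratings exist only for scheduled visits: Appendix A includes the assessment at unscheduled visits, and SAP Section 4.4 brings those visits into the analysis windows. All this stands. What remains is that each of these routes is reactive or discretionary.

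**The site would know.** A start is conditional on the investigator's judgement of benefit and risk, which largely implies knowledge beforehand. This too stands, so the documents do not support a claim that the site is left unaware. The timing of that judgement is still worth stating, because Section 4.7.2 notes that some of these drugs need no prescription and that it counts tryptophan and 5-HTP supplements among them.

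**Section 7.1.3.2 can be read more widely.** Its opening sentence is not limited to visits and could leave extra timing to the investigator. Section 6.2.3.2 gives the same instruction and does tie it to each visit, so the wider reading is not secure.

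**The LMTM comparison is imperfect.** Section 2 presents Week 2 as a general safety assessment, not as an interaction check. Two weeks is therefore a practical interval borrowed from the schedule; nothing in the documents shows that it is the right one for every serotonergic drug.

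**LMTM dose increases.** An increase is allowed from Visit 3, so one might ask for a hold on increases after a serotonergic start. Increases occur only at dispensing visits, where the subject is examined anyway. A hold would also leave untouched an increase at Visit 3 followed by a start a few days later. I do not recommend it.

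**Importance is not quantified.** The documents give neither a number of starts nor a rate of serotonin toxicity in this study, and Section 4.7.2 describes the MAO inhibition as an in vitro finding. This limits the weight of the point.

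**Conclusion.** The gap is real and limited. The protocol stresses monitoring when a serotonergic drug is begun, yet it allows such starts only where scheduled examinations are 91 days apart (63 to 119 within windows) and no scheduled call remains. Detection before the next visit rests on caregiver-initiated contact or investigator discretion.

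Deferring starts to Week 13 is sensible, because it separates the two drug starts. What is missing is a timed contact afterwards. The documents do not support reading this as the absence of a safeguard or as evidence of harm; it is a cheap improvement that should be made.

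The intervals follow directly from the visit schedule. The 45.5-day mean and the 15.4% rest on the even-spread assumption. The Investigator's Brochure, which holds the drug list and half-lives, was not available and might contain further guidance.

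**What to change.** At the next protocol amendment:

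- **Section 4.7.2, contact.** Require a documented site contact about 2 weeks after any serotonergic start. The caregiver is asked about those signs on the existing serotonin form that a caregiver can report, such as agitation, insomnia, tremor, shivering, sweating, diarrhea, fever and incoordination. Any new sign leads to an unscheduled visit for examination and vital signs.
- **Section 4.7.2, sequence.** State that the investigator's benefit/risk judgement is made before the drug is started, so the site must know of the planned start.
- **Section 4.7.5, footnote 3.** State that the monitoring steps for bedtime trazodone include this contact.

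**Cost.** A few sentences and one call per start, with existing staff and an existing form. For scale only, if 5% to 15% of 1050 to 1400 subjects each had one start (an assumed range), the calls would number from 0.05 × 1050 = 52.5, about 53, to 0.15 × 1400 = 210. The study is open-ended and subjects may start more than one such drug, so the count could be higher.

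**Downside.** Some calls will lead to unscheduled visits for non-specific signs. A call still relies on what the caregiver notices and cannot detect clonus, hyperreflexia, mydriasis or other signs that need examination.
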